#### 11.3.1.3 Faecal calprotectin, CRP levels and ESR

Absolute values and change from BIS and from BOLS to each post BOLS timepoint will be presented using descriptive statistics for faecal calprotectin, CRP and ESR levels (*Table 14.2.3.1 and 14.2.3.2*).

#### 11.3.1.4 SF-36 Questionnaire

Absolute values and change from BIS and from BOLS to each post BOLS timepoint for total score will be presented using descriptive statistics for SF-36 Questionnaire scores (*Table 14.2.4.1 and 14.2.4.2*). SF-36 Questionnaire is assessed at the following visits: D28, D56/M2, and M3 to M24 on a monthly basis.

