2.4. Secondary Endpoints

The secondary endpoints of this study are:

- The change from Day 0 in Total Mayo Score.
- The change from Day 0 in Partial Mayo Score.
- The time to UC worsening.
- The change from Day 0 in fecal calprotectin, CRP levels and ESR.
- The scores and changes from Day 0 in SF-36 Questionnaire scores.
- The miR-124 expression at month 12, month 36 and month 48.
- The number of incidences of treatment-emergent serious adverse events.
- The number of incidences of treatment-emergent adverse events of special interest.
- The number of incidences of adverse events leading to investigational product discontinuation.
- The number of incidences of specific laboratory abnormalities.
- Percentage of subjects reaching clinical remission at M12, M36, and M48.
- Percentage of subjects reaching clinical response at M12, M36, and M48.
- Percentage of subjects reaching endoscopic improvement at M12, M36, and M48.
- Percentage of subjects reaching endoscopic remission at M12, M36, and M48.
- Percentage of subjects reaching corticosteroid-free clinical remission at M12, M36, and M48.

The echocardiography secondary endpoints^[9] are:

- Absolute (%) change-from-previous echocardiogram of Left ventricle Ejection Fraction (LVEF) as measured by 2-dimensional echocardiography
- Number of subjects with a clinically relevant reduction (change-from-previous echocardiogram) of LVEF, defined as by > 10% reduction (absolute percentage points) to a value < 50%

- Absolute (%) change in Global Longitudinal Strain (GLS) from-previous echocardiogram
- Number of subjects with a relative percentage reduction in GLS by > 15% from the previous value
- Number of subjects with a reduction of LVEF > 10% (absolute percentage points) to a value $\geq 50\%$ with an accompanying fall in GLS > 15%
- Number of subjects with reduction in LVEF by > 10% (absolute percentage points) to a value $\geq 50\%$
- Changes from previous echocardiography of other echocardiographic parameters as described in a standard protocol, including 2-dimensional volumes, RV size and systolic function and valve function.

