5.3.7. SF-36 questionnaire (SF-36)

The SF-36 questionnaire is a self-administered questionnaire containing 36 items which takes about five minutes to complete. It measures health on eight multi-item dimensions, covering functional status, well-being, and overall evaluation of health. SF-36 will be filled in by the subjects on a monthly basis until M24 prior to any study procedures.

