Appendix 2 : SF-36 Questionnaire (English Version)

Your Health and Well-Being

This survey asks for your views about your health. This information will help keep track of how you feel and how well you are able to do your usual activities. Thank you for completing this survey!

For each of the following questions, please mark an in the one box that best describes your answer.

1. In general, would you say your health is:

Excellent	Very good	Good	Fair	Poor
 1	 2	 3	 4	 5

2. Compared to one year ago, how would you rate your health in general now?

Much better now than one year ago	Somewhat better now than one year ago	About the same as one year ago	Somewhat worse now than one year ago	Much worse now than one year ago
 1	 2	 3	 4	 5

3. The following questions are about activities you might do during a typical day. Does your health now limit you in these activities? If so, how much?

Yes, limited a lot	Yes, limited a little	No, not limited at all
 1	 2	 3

a Vigorous activities, such as running, lifting heavy objects, participating in strenuous sports..... 1 2 3

b Moderate activities, such as moving a table, pushing a vacuum cleaner, bowling, or playing golf..... 1 2 3

c Lifting or carrying groceries..... 1 2 3

d Climbing several flights of stairs..... 1 2 3

e Climbing one flight of stairs..... 1 2 3

f Bending, kneeling, or stooping..... 1 2 3

g Walking more than a mile..... 1 2 3

h Walking several hundred yards..... 1 2 3

i Walking one hundred yards..... 1 2 3

j Bathing or dressing yourself..... 1 2 3

4. During the past 4 weeks, how much of the time have you had any of the following problems with your work or other regular daily activities as a result of your physical health?

	All of the time	Most of the time	Some of the time	A little of the time	None of the time
--	-----------------	------------------	------------------	----------------------	------------------

- a Cut down on the amount of time you spent on work or other activities..... 1..... 2..... 3..... 4..... 5
- b Accomplished less than you would like 1..... 2..... 3..... 4..... 5
- c Were limited in the kind of work or other activities 1..... 2..... 3..... 4..... 5

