- d Had difficulty performing the work or other activities (for example, it took extra effort) 1..... 2..... 3..... 4..... 5

5. During the past 4 weeks, how much of the time have you had any of the following problems with your work or other regular daily activities as a result of any emotional problems (such as feeling depressed or anxious)?

	All of the time	Most of the time	Some of the time	A little of the time	None of the time
--	-----------------	------------------	------------------	----------------------	------------------

- a Cut down on the amount of time you spent on work or other activities..... 1..... 2..... 3..... 4..... 5
- b Accomplished less than you would like 1..... 2..... 3..... 4..... 5
- c Did work or other activities less carefully than usual..... 1..... 2..... 3..... 4..... 5

6. During the past 4 weeks, to what extent has your physical health or emotional problems interfered with your normal social activities with family, friends, neighbors, or groups?

	Not at all	Slightly	Moderately	Quite a bit	Extremely
--	------------	----------	------------	-------------	-----------

7. How much bodily pain have you had during the past 4 weeks?

	None	Very mild	Mild	Moderate	Severe	Very severe
--	------	-----------	------	----------	--------	-------------

8. During the past 4 weeks, how much did pain interfere with your normal work (including both work outside the home and housework)?

	Not at all	A little bit	Moderately	Quite a bit	Extremely
--	------------	--------------	------------	-------------	-----------

9. These questions are about how you feel and how things have been with you during the past 4 weeks. For each question, please give the one answer that comes closest to the way you have been feeling. How much of the time during the past 4 weeks...

	All of the time	Most of the time	Some of the time	A little of the time	None of the time
a Did you feel full of life?	 1	 2	 3	 4	 5
b Have you been very nervous?	 1	 2	 3	 4	 5
c Have you felt so down in the dumps that nothing could cheer you up?	 1	 2	 3	 4	 5

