| Change from BIS to Visit | n
Mean
Etc  | xx (xx.x %)
xx.xx  | xx (xx.x %)
xx.xx  |

Version Date 20 MAY 2021

Template STATt004

Page 43 of 97

|                           |      |             |             |             |
|---------------------------|------|-------------|-------------|-------------|
| Change from BOLS to Visit | n    | xx (xx.x %) | xx (xx.x %) | xx (xx.x %) |
|                           | Mean | xx.xx       | xx.xx       | xx.xx       |
|                           | Etc  |             |             |             |
|                           | Etc  |             |             |             |

---

The denominator for each percentage is the number of patients within the column.

BIS: Day 0 of ABX464-101 study

BOLS: Day 56 of ABX464-101 study

---

Source: Listing 16.2.6.3

Path\Filename

Page x/y

*Programming Note: Parameters to be included: Faecal Calprotectin, CRP and ESR.*

*Please present subgroups in the following order:*

- All patients
- Patients being in clinical response at Baseline Open-Label Study (BOLS)
- Patients not being in clinical response at Baseline Open-Label Study (BOLS)
- Patients previously treated with biological drugs
- Patients naive from biological drugs

This layout also applies to:

*Table 14.2.3.2 Change from Baseline: Faecal Calprotectin, CRP and ESR (NRI Set)*

ABX464-102

ddMMMyyyy HH:MM

Table 14.2.4.1 Change from Baseline: SF-36 Questionnaire (OC Set)

<Subgroup>

|                          |           | 50mg ABX464 (101) + | Placebo (101) +   |               |
|--------------------------|-----------|---------------------|-------------------|---------------|
|                          |           | 50mg ABX464 (102)   | 50mg ABX464 (102) | Total         |
|                          |           | (N=xx)              | (N=xx)            | (N=xx)        |
| BIS                      | n         | xx (xx.x %)         | xx (xx.x %)       | xx (xx.x %)   |
|                          | Missing   | xx (xx.x %)         | xx (xx.x %)       | xx (xx.x %)   |
|                          | Mean      | xx.xx               | xx.xx             | xx.xx         |
|                          | 95% CI    | xx.xx – xx.xx       | xx.xx – xx.xx     | xx.xx – xx.xx |
|                          | SD        | xx.xx               | xx.xx             | xx.xx         |
|                          | Minimum   | xx.x                | xx.x              | xx.x          |

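### The SF-36 is analysed only as one total score with no scoring rule, although the protocol describes eight dimensions and the printed item codes run in both directions

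*SAP*

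**What the plan says.** Quality of life measured by the SF-36 up to M24 is a secondary objective (Protocol 2.2, SAP 2.2). The endpoint in Protocol 2.4 is "The scores and changes from Day 0 in SF-36 Questionnaire scores", and SAP 4.2 repeats it. On the instrument itself, Protocol 5.3.7 says: "It measures health on eight multi-item dimensions, covering functional status, well-being, and overall evaluation of health".

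The analysis is in SAP 11.3.1.4: absolute values and changes from both baselines (BIS and BOLS) "for total score will be presented using descriptive statistics for SF-36 Questionnaire scores". The output shells agree. Table 14.2.4.1, "Change from Baseline: SF-36 Questionnaire (OC Set"), has a single block of baseline, visit and change rows with no dimension label, and Table 14.2.4.2 uses the same layout. Listing 16.2.6.4 shows the answer to each question and then one row for the total.

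Neither document says how the total is formed. SAP 11.3 promises listings of the SF-36 derivations but gives no derivation. SAP 10.4 applies LOCF to missing continuous values and rules out any other imputation, so nothing covers a missing item. SAP section 13 cites no references.

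**The concern.** A single total needs two things that the plan does not supply.

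The first is a common direction. In Protocol Appendix 2, "In general, would you say your health is" is coded 1 for the best answer and 5 for the worst. "Vigorous activities, such as running, lifting heavy objects, participating in strenuous sports" is coded 1 for the most limited and 3 for not limited. The clash also occurs inside one question block: "Did you feel full of life" and "Have you been very nervous" share the same frequency codes, so a higher code is worse for one and better for the other. Without a recoding rule, a reader of Table 14.2.4.1 cannot tell whether a positive change is improvement.

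The second is a reason to combine the dimensions. A total cannot show which of the eight moved. SAP 11.3.1.1 treats the Mayo score differently: it defines four versions by their items and tabulates every component.

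At stake is the only planned summary for a named secondary objective. It could be reported with an unknown direction, or could show no change when dimensions moved in opposite directions.

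**Working it through.** The plan states no SF-36 range or reference value, so there is no figure to reproduce. The check asks what a plain sum of the Appendix 2 codes would do.

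**Inputs.** Numeric codes are legible for 29 of the 36 items: Q1, Q2, Q3a–j, Q4a–d, Q5a–c, Q9a–i and Q10. For Q6, Q7, Q8 and Q11a–d the available text shows no codes. That is a limit of the text as read, not a fault in the plan. For those seven items I assume codes from 1 upward, left to right, as elsewhere.

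**Formula.** Raw sum = sum of item codes. For an item with L levels, best health contributes L where a higher code is better and 1 where it is worse. Worst health contributes the reverse. The lowest possible sum takes 1 per item; the highest takes L per item.

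| Items | Levels | Higher code means | Worst health | Best health | Lowest sum | Highest sum |
|---|---|---|---|---|---|---|
| Q1, Q2 | 5 | worse | 10 | 2 | 2 | 10 |
| Q3a–j | 3 | better | 10 | 30 | 10 | 30 |
| Q4a–d | 5 | better | 4 | 20 | 4 | 20 |
| Q5a–c | 5 | better | 3 | 15 | 3 | 15 |
| Q9a, d, e, h | 5 | worse | 20 | 4 | 4 | 20 |
| Q9b, c, f, g, i | 5 | better | 5 | 25 | 5 | 25 |
| Q10 | 5 | better | 1 | 5 | 1 | 5 |
| **29 items, codes legible** | | | **53** | **101** | **29** | **125** |
| Q6, Q8 (assumed) | 5 | worse | 10 | 2 | 2 | 10 |
| Q7 (assumed) | 6 | worse | 6 | 1 | 1 | 6 |
| Q11a, c (assumed) | 5 | better | 2 | 10 | 2 | 10 |
| Q11b, d (assumed) | 5 | worse | 10 | 2 | 2 | 10 |
| **All 36 items** | | | **81** | **116** | **36** | **161** |

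**Results without recoding.**

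- 29 items: 23 run higher-is-better and 6 higher-is-worse. Worst to best health spans 101 − 53 = 48 of 125 − 29 = 96 points, or 50%.
- 36 items, with the assumed codes: 25 run higher-is-better and 11 higher-is-worse. The span is 116 − 81 = 35 of 161 − 36 = 125 points, or 28%.
- In both cases neither end of the scale corresponds to best or worst health.
- Q9, using legible codes only: worst health gives 20 + 5 = 25 and best gives 4 + 25 = 29. The whole nine-item block moves by 4 points.
- A one-category improvement on each higher-is-worse item lowers the sum by 6 (29 items) or 11 (36 items, assumed codes).

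**Result with recoding.** If every item is turned so that higher is better, the 36-item sum runs from 36 (worst) to 161 (best), and direction is restored. Merging remains: one category worse on each of Q4a–d (−4) with one category better on Q9b, c, f and g (+4) gives a change of zero.

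**The case against.** The strongest objection is that the arithmetic tests a rule the SAP does not state. A reader might infer that the items will be added as coded, making the result certain to be uninterpretable. The documents do not support that. SAP 11.3.1.4 gives no formula, and SAP 11.3 expects some derivation. The 50% and 28% figures show what the text permits, not what will be done.

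A reader might also treat the 36-item figures as read from Appendix 2. Seven of those items rest on assumed codes, and so does any statement about Q11. The 29-item result does not need that assumption.

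A third tempting inference is that the protocol endpoint is the eight dimensions and that SAP 1.2 conceals a change. Protocol 2.4 does not mention dimensions. They appear in Protocol 5.3.7, which describes the instrument rather than its analysis, and the plural in the endpoint could refer to visits or subjects. An undeclared departure from protocol is not established.

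Finally, the consequence is limited. SAP 10.1 presents all variables descriptively, 22 patients entered (Protocol 1.3), SF-36 collection stops at M24, and item answers are listed by patient and visit, so dimension scores could be derived later.

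These objections limit the size and certainty of the claim. They do not supply a scoring rule or explain why eight dimensions should be reported as one number. SAP section 15 lets the programmer adapt layouts, but that does not define the analysed variable.

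**Conclusion.** The point holds in this form: the SAP fixes one SF-36 total as the only analysed variable and does not define it, for an instrument that the protocol describes as eight-dimensional and whose legible codes run both ways. Those facts need no assumption.

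The size is conditional. If items are summed unrecoded, worst-to-best health covers 50% of the possible range on the 29 legible items, or 28% on all 36 if the remaining seven are coded left to right from 1. If items are recoded, the direction problem goes and only the merging of dimensions remains.

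The SAP should be changed, but the trial's main conclusion does not depend on it: the endpoint is secondary and descriptive, and the primary safety endpoint is untouched.

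**What to change.** In SAP 11.3.1.4, replace the total with the eight dimension scores as the analysed variables. Name the SF-36 version and scoring manual; this is necessary because neither document says which items form which dimension. State the recoding so that higher means better, the range of each score, and the rule for missing items, and reconcile that rule with SAP 10.4.

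Show values and changes from BIS and BOLS for each dimension in Tables 14.2.4.1 and 14.2.4.2, and add the dimension scores to Listing 16.2.6.4. Remove the total, or keep it beside the dimensions with a definition and a justification in the SAP.

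The cost is SAP and shell wording, scoring code, and eight blocks where each table now has one. With two analysis sets and five presentations each (all patients plus four subgroups), that is 2 × 5 × 8 = 80 blocks instead of 10. No new data are needed. Protocol section 9 allows documented SAP amendments before final database lock.

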### 11.3.1.5 miR-124

Quantification of miR-124 expression in total blood will be measured at Month 12, Month 36 and Month 48 and will not be analysed by Simbec-Orion. It will be detailed in a separate report.

### 11.3.1.6 Clinical remission, corticosteroid-free clinical remission and clinical response

**Clinical remission** is achieved when all the following criteria are met in the components of the Mayo Score:

- rectal bleeding sub-score = 0
- central or local endoscopy sub-score <= 1
- stool frequency sub-score <= 1.

**Corticosteroid-free clinical remission** is defined as clinical remission and concomitant corticosteroid free for  $\geq$  90 days prior to these timepoints among patients with clinical remission after 8 weeks of induction treatment (at baseline of ABX464-102 study).

**Clinical response** is defined as:

- reduction in Modified Mayo Score of at least 2 points and  $\geq$  30 percent from BIS
- with an accompanying decrease in rectal bleeding sub-score of  $\geq$  1 point or absolute rectal bleeding sub-score of  $\leq$  1 point.

Proportion of patients (n and percentage) will be presented for patients achieving clinical remission, corticosteroid-free clinical remission and clinical response at M12, M24, M36 and M48 (*Table 14.2.5.1 and 14.2.5.2*).

In addition, shift tables will be presented showing changes from BIS to each post baseline visit and from BOLS to each post baseline visit (*Table 14.2.5.3 and 14.2.5.4*) for clinical remission.

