5.3.9. Sigmoidoscopy

A Sigmoidoscopy will be performed in all subjects at Day 56/M2, Month 24, Month 36, and Month 48 (i.e. Study procedure).

In addition, monthly sigmoidoscopies could be performed if deemed necessary by the investigator (Until month 24). In such a case, the endoscopy rating will be reported in the eCRF (Total MCS).

Sigmoidoscopies procedures (or colonoscopies if applicable) at Month 24, Month 36, and Month 48 will be standardized for optimized video acquisition at clinical sites. Sigmoidoscopies should be performed according to the Central Imaging Management System Charter. Central Imaging Management System will be provided including a central image database. Once uploaded, video data will be analyzed for quality and resolution prior to independent review by an expert central reader. Study videos will be scored separately using the Mayo Clinic Score (excluding friability) for all time points by central readers.

The local reading result of sigmoidoscopy need to be available on M48 visit to check eligibility to enter study ABX464-108. The sigmoidoscopy can be performed within 14 days before the visit but not after the visit. If the sigmoidoscopy results (local reading) are not available on M48, the patient will be considered not eligible to enter the ABX464-108 study and will performed the end of study visit 28 days (+4 days) after M48.

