5.3.10. Clinical remission, clinical response, and corticosteroid-free clinical remission

The following remission and response will be assessed at M12, M24, M36 and M48:

Clinical remission is achieved when all the following criteria are met in the components of the Mayo Score:

- rectal bleeding sub-score = 0
- central endoscopy sub-score <= 1
- stool frequency sub-score <= 1.

Clinical response is defined as:

- reduction in Total Mayo Score of at least 2 points and >= 30 percent from baseline
- with an accompanying decrease in rectal bleeding sub-score of >= 1 point or absolute rectal bleeding sub-score of <= 1 point.

Corticosteroid-free clinical remission is defined as clinical remission at M12, M24, M36 and M48, and concomitant corticosteroid free for ≥ 12 weeks prior to these timepoints among patients with clinical remission after 8 weeks of induction treatment (at baseline of ABX464-102 study).

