### 1.2 CHANGES FROM PROTOCOL

- The echocardiography secondary endpoints will be included in a separate report.
- Sustained clinical remission and sustained endoscopic remission/improvement will be summarized as part of the secondary endpoints.
- Observed Cases (OC) Set and Non-responder Imputation (NRI) Set are defined for populations instead of the populations defined in the protocol.
- In the definition of corticosteroid-free clinical remission (Section 11.3.1.6), time interval is changed from 12 weeks to 90 days for consistency with other Abivax studies.
- In the definition of clinical response (Section 11.3.1.6), Modified Mayo Score is used instead of Total Mayo Score for consistency with other Abivax studies.
- All efficacy variables will be summarized based on the following subgroups:
  - Patients being in clinical response at BOLS and not being in clinical response at BOLS
  - Patients previously treated with biological drugs and naive from biological drugs.
- In the Synopsis and Section 2.4 of the protocol, M24 is missing from the list of timepoints for clinical remission, clinical response, endoscopic improvement, endoscopic remission and corticosteroid-free clinical remission inconsistently with further sections. This timepoint is included in the current SAP to ensure that these secondary endpoints are analysed for all required timepoints.

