## 11.2 PATIENT CHARACTERISTICS AT BASELINE

### 11.2.1 Demographic and Baseline Characteristics

Demographics and other baseline characteristics will be summarized by treatment group (*Table 14.1.3*). This analysis will be conducted on the OC Set.

Age will be calculated using Year of Birth and Date of first treatment and presented as age at last birthday as an integer.

Body Mass Index (BMI) is the patient's body weight in kilograms divided by the square of the patient's height in metres.

Age, gender, childbearing potential, race, height, weight and BMI will be summarised using the OC Set.

In addition to demographic and baseline characteristics, disease characteristics (at Day 0) including Total and Modified Mayo score (TMS and MMS), faecal calprotectin, percentage of subjects with concomitant Corticosteroid, clinical remission, corticosteroid-free clinical remission, clinical response, endoscopic remission, endoscopic improvement will also be summarized using the OC Set.

Clinical remission, corticosteroid-free clinical remission, clinical response, endoscopic remission and endoscopic improvement are defined in Section 11.3.1.6 and 11.3.1.7.

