#### 11.3.1.1 Mayo Score

The **Total Mayo score** (TMS) consists of 4 items: stool frequency, rectal bleeding, flexible sigmoidoscopic examination, and a physician global assessment of disease activity (see protocol Appendix 3).

A non-invasive 9-point Mayo or **partial Mayo Score** (pMS) incorporates stool frequency, rectal bleeding, and the physician's global assessment of disease activity. The partial Mayo Score has been found to correlate closely with the full Mayo score and to independently have strong discriminative and construct validity and responsiveness to change in disease activity. Either the Partial or the Total Mayo score will be completed at each subject visit by the Investigator.

**Modified Mayo Score** (MMS) consists of 3 items: stool frequency, rectal bleeding, flexible sigmoidoscopic examination.

**Partial Modified Mayo Score** (pMMS) consists of only 2 items: stool frequency and rectal bleeding. MMS or pMMS will also be used in descriptive analysis and for efficacy evaluation.

Absolute values and change from BIS and from BOLS to each post BOLS timepoint will be presented using descriptive statistics for Total Mayo Score (TMS), Partial Mayo Score (pMS), Modified Mayo Score (MMS) and partial Modified Mayo Score (pMMS) (*Table 14.2.1.1 and 14.2.1.2*) and for the different components of the Total Mayo Score (stool frequency, rectal bleeding, physician rating of disease activity and mucosal appearance at endoscopy – central reading) (*Table 14.2.1.3 and 14.2.1.4*).

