### 11.3.1.7 Endoscopic improvement and endoscopic remission

**Endoscopic improvement** is achieved if the Mayo central endoscopic sub-score is 0 or 1.

**Endoscopic remission** is defined as Mayo central endoscopic sub-score = 0.

Endoscopic improvement and remission (central reading sub-score) will be presented as proportion of patients (n and percentage) (*Table 14.2.6.1 and 14.2.6.2*).

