### 11.3.1.8 Sustained clinical remission and sustained endoscopic remission/improvement

**Sustained clinical remission** is defined as clinical remission at the given timepoint (M12, M24, M36 or M48) with clinical remission at BOLS.

**Sustained endoscopic improvement** is defined as endoscopic improvement at the given timepoint (M12, M24, M36 or M48) with endoscopic improvement at BOLS.

**Sustained endoscopic remission** is defined as endoscopic remission at the given timepoint (M12, M24, M36 or M48) with endoscopic remission at BOLS.

Sustained clinical remission and sustained endoscopic improvement/remission will be presented as proportion of patients (n and percentage) (*Table 14.2.7.1 and 14.2.7.2*).

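### SAP 11.3.1.6 lets a local endoscopy score satisfy clinical remission where the protocol requires a central one, undeclared and with no order of precedence; the reading behind the M12 endoscopic endpoints is also left open

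*SAP*

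**What the plan says.** Protocol 5.3.10 builds clinical remission from three Mayo components; the endoscopic one is "central endoscopy sub-score <= 1". SAP 11.3.1.6 keeps the other two and changes this one to "central or local endoscopy sub-score <= 1". SAP 1.2 lists two other changes to definitions in that same SAP section: the steroid-free interval and, for clinical response, "Modified Mayo Score is used instead of Total Mayo Score for consistency with other Abivax studies". It does not mention the endoscopy reader.

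Elsewhere the SAP stays with the central reader. In 11.3.1.7, endoscopic improvement "is achieved if the Mayo central endoscopic sub-score is 0 or 1", and endoscopic remission is a central score of 0. The Table 14.2.6.1 footnote repeats the central basis, and the component summary in 11.3.1.1 shows "mucosal appearance at endoscopy – central reading". No reader is named for the endoscopy item inside the Total or Modified Mayo Score.

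The definition is reused. SAP 11.3.1.8 defines sustained clinical remission as "clinical remission at the given timepoint (M12, M24, M36 or M48) with clinical remission at BOLS". Corticosteroid-free remission is restricted to patients in remission at the open-label baseline. SAP 11.2.1 applies the definitions at baseline; its list starts with clinical remission and ends "endoscopic remission and endoscopic improvement are defined in Section 11.3.1.6 and 11.3.1.7".

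On timing, Protocol 2.4 sets the endoscopic endpoints at M12, M36 and M48, and SAP 1.2 adds M24. Protocol 5.2.3 and 5.3.9 require scopes at D56/M2, M24, M36 and M48 and leave other scopes up to M24 to the investigator. Standardised video is named for M24, M36 and M48 only. Protocol 5.3.9 also says "Study videos will be scored separately using the Mayo Clinic Score (excluding friability) for all time points by central readers". SAP 11.3 lets the nearest unscheduled scope within a month stand in for a scheduled one that was missed.

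**The concern.** A definition has changed between protocol and SAP without being declared, and the new wording supports two derivations. One programmer could pass a patient if either reading is 1 or less. Another could use the local reading only when the central one is absent. The two can give different remission rates from the same data.

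Under the first derivation the outputs can disagree about one patient: remission in Table 14.2.5.1, but no endoscopic improvement in Table 14.2.6.1. Sustained and corticosteroid-free remission carry the ambiguity twice, at the visit and at BOLS. Clinical response has a related gap, because it rests on a Modified Mayo Score with no named reader. That also affects the subgroups in SAP 10.7 that are split by response at BOLS.

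At M12 the endoscopic endpoints need a central score from a visit with no scheduled scope.

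**Working it through.** **Step 1. The two rules side by side.**

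| Central | Local | Protocol 5.3.10 | SAP, either suffices | Central first, local if none |
|---|---|---|---|---|
| ≤ 1 | ≤ 1 | met | met | met |
| ≤ 1 | ≥ 2 | met | met | met |
| ≥ 2 | ≤ 1 | not met | **met** | not met |
| ≥ 2 | ≥ 2 | not met | not met | not met |
| none | ≤ 1 | not assessable | met | met |
| none | ≥ 2 | not assessable | not met | not met |

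No row turns a protocol remitter into a non-remitter. The number in remission can therefore only stay the same or rise, and so can the percentage on the fixed column denominator of Table 14.2.5.1. Row 3 is where the two readings of the SAP part, and it is also the row that fails central-only endoscopic improvement.

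**Step 2. Patient counts (Protocol 1.3).** Enrolled: 15 + 7 = 22. M12 per-protocol set: 22 − 3 = 19, which reproduces the stated figure. M12 scopes: 16. Attended M12 but not scoped: 19 − 16 = 3. Enrolled without an M12 scope: 22 − 16 = 6 (27.3%).

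**Step 3. Weight of one row-3 patient who meets the other criteria**, taking the OC Set as all 22:
- total column: 1/22 = 4.5 points
- former ABX464 group: 1/15 = 6.7 points
- former placebo group: 1/7 = 14.3 points

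The documents give no reader-disagreement rate. For an assumed 0 to 3 such patients, the total rate rises by 0 to 3/22 = 13.6 points.

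As an illustration, take the 12 M12 remitters in Protocol 1.3 and suppose d of them are row-3 patients. The either-suffices rate is 12/22 = 54.5% (exact 95% CI 32.2 to 75.6). The central-only rate is (12 − d)/22:
- d = 1: 11/22 = 50.0% (28.2 to 71.8)
- d = 3: 9/22 = 40.9% (20.7 to 63.6)

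The interim text does not name the reader, so d is an assumption.

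**Step 4. M12 endoscopic improvement.** Under the shell the rate is k/22, where k is the number of M12 scopes with a central score of 0 or 1. Protocol 1.3 reports all 16 scopes at 0 or 1 but names no reader. If all 16 were centrally read with that result, the rate is 16/22 = 72.7% (49.8 to 89.3). Each scope without a qualifying central score removes 4.5 points; k = 8 would give 8/22 = 36.4%. The one-month substitution in SAP 11.3 does not settle this, because it covers scheduled scopes and names no reader.

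**Step 5. Denominators.** OC Table 14.2.5.1 divides by all patients in the column; OC Table 14.2.5.3 divides by non-missing observations. If the interim definition matches the SAP, M12 clinical remission appears as 12/22 = 54.5% in the first and 12/16 = 75.0% (47.6 to 92.7) in the second.

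**The case against.** The strongest reply is that the SAP meant the local score as a fallback. That is plausible, and under it row 3 causes no inflation. Listing 16.2.6.1 prints both readings, so any discordant patient can be traced. This stands as a limit on the size of the problem. It does not remove the problem, because neither document states that order.

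A reader might infer that the reported remission rate will be inflated. The documents do not support that: no count of discordant patients exists, and it may be zero.

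A reader might infer that M12 scopes were not centrally read, so that the M12 endoscopic endpoints collapse to 0/22. That is also unsupported. Protocol 5.3.9 refers to central scoring at all time points, 16 of the 19 patients in the M12 set were scoped, and earlier visit schedules are not visible. Only *not confirmed* can be said.

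A reader might take the exclusion of friability from central scoring as a reason why local scores would run lower. The phrase is not defined here. The rule that friability scores 2 or 3 belongs to a note on ABX464-103, and the words could equally mean that friability is not scored. No direction follows.

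A reader might think that a poor M12 result could not be told from a missing one. The OC shells print No and Missing on separate rows, so it can.

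Finally, the column denominator does not breach SAP 10.1, whose default gives way where a table specifies otherwise.

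**Conclusion.** The point holds. The change of reader is real, undeclared and without precedence, and read literally it lets a local score override a central score of 2 or more. Each discordant patient is worth 4.5 points in the total column and 6.7 or 14.3 in the group columns, assuming all 22 enrolled patients are in the OC Set. How many there are is unknown, and the discordance effect is zero under a central-first reading.

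The upward-only direction is established for the number in clinical remission and for its rate on a fixed denominator. On a non-missing denominator, patients with only a local score enter both parts of the fraction, so the direction is open.

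The M12 gap is real only in the sense that central reading there is unconfirmed. The denominator difference is a point of presentation.

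These are descriptive secondary endpoints in a safety study. The risk is a rate that two analysts would not reproduce, not a wrong test. It should be fixed before database lock.

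**What to change.** (a) In SAP 11.3.1.6, use the central sub-score wherever one exists for the visit and the local score only when there is none. Apply the same rule to remission at BOLS and to the endoscopy item of the Total and Modified Mayo Scores in 11.3.1.1, so that clinical response follows it. Add a central-only sensitivity row for remission and declare the change in SAP 1.2.

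(b) At M12, report the number scoped and the number centrally read. Show endoscopic improvement and remission by central and by local reading, labelled as resting on scopes that the current protocol does not schedule. List this in SAP 1.2, since Protocol 5.3.11 is central only. In 11.3.1.8, state which reading defines endoscopic status at BOLS; these documents do not say whether ABX464-101 scopes were centrally read.

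(c) Optional: use the non-missing denominator in the OC proportion tables (14.2.5.1, 14.2.6.1, 14.2.7.1) and keep the NRI tables on all 22.

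The cost is SAP wording, entries in 1.2 and a few table rows, repeated for all patients and the four subgroups. For (c), the OC and NRI tables share one layout, so their footnotes must be split. Both readings are already columns in Listing 16.2.6.1, so no new reads are needed. The remission rate may come out lower than under the either-suffices reading. The M12 by-reader results will not be directly comparable with M24 to M48. Any OC rate on scoped patients alone must stay beside the NRI rate, because those scopes may be selective.
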